Participants will be selected with assistance from Sanders Brown Center on Aging (SBCoA) staff using the University of Kentucky Alzheimer's Center Longitudinal participant database (IRB# 88-0102-F2L [[name], PI]). University of Kentucky Alzheimer's Disease Center Clinical Core Leader, [name], has approved access to and use of the University of Kentucky Alzheimer's Disease Center Community Registry database, which is located at the SBCoA Clinic, [name]. The database follows 200-300 volunteers who live in the local community around SBCoA Clinic for longitudinal data collection purposes. Participants with cognitive impairment are primary targets for data tracking for the database. Each participant in the database has corresponding information for primary caregivers, which is also maintained in the database. All cognitively impaired database enrollees and their caregivers have agreed to be contacted by SBCoA associates for invitation to participate in additional research projects. Annual confirmation is obtained by the center to ensure participants continue to permit contact via phone calls or other methods from researchers and staff at SBCoA for notification, explanation, and invitation to additional research opportunities offered by the University of Kentucky.

Patients of the Kentucky Neuroscience Institute with memory impairment may also be contacted for participation of this study. Upon identification of eligible participants, the KNI medical team will determine patient interest to be contacted by study personnel and notify [name] (PI) to follow up with contact to potential participants and/or the study flyer will be mailed or emailed to eligible patients with request to contact study personnel if interested in study participation.

Primary measures:

Feasibility will be assessed by monitoring of protocol adherence and behavior change.

- Caregivers will be responsible for providing treatment protocols throughout duration of treatment window. Adherence to the protocol will be kept and measured using the behavioral journal and intervention adherence log
- Weekly check-ins with the caregivers will provide opportunity to review adherence and reactions to the protocol, as well as assess for adverse reactions, need for modification, or discontinuation. If the investigator finds that the participant is noncompliant, the PI

may remove the participant from further participation in the study.

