- Caregiver burden will be measured using the Zarit Caregiver Burden Scale.

Secondary measures:

- Behavior will be assessed using the Vineland Adaptive Behavior Scales (VABS) and the Neuropsychiatric Inventory (NPI) at baseline and post-intervention, and behavior tracking throughout intervention.
- Cognitive measures will include the MOCA and CDR at baseline, post-intervention and follow up
- Heart rate tracking and sleep will be measured using wearable activity tracker (Actigraph) at all times except while charging device.

Sensory processing patterns and functional activity engagement will be assessed for all participants with dementia and used for individualization arm of intervention.

- Sensory processing will be measured using the Adult Sensory Profile (ASP) for all subjects at baseline.
- Functional activity engagement will be measured using the Canadian Occupational Performance Measure (COPM) at baseline and post-intervention.

**Control Group:** Standard of care for behavioral management and 2-page educational pamphlet describing safety for home environments. At the conclusion of the study, following the four-week follow up visit, participants will be offered a standardized sensory kit (as described below) to use at their discretion.

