Once eligibility is confirmed, the research assistant will email a REDCap link to the caregiver for the Zarit Caregiver Burden and the Adult Sensory Profile, Actigraph and charger, and a copy of consent forms to the participant's caregiver. The PI will complete the COPM on visit 1, and provide caregiver and participant with Actigraph wear and care instructions. The VABS will be emailed to the caregiver via a confidential link through Pearson Publishing.

Subjects will be randomized to treatment arms by the statistical team. Participants will be randomized into one of the three groups: control, standard environmental design protocol, individualized environmental design protocol. Recruitment will be ongoing until all groups have 10 participants. In the event of drop out or early termination (causes will be recorded), researchers will recruit for replacement participants so that the study is completed with 30 entire study duration cases.

Visit 2 will consist of baseline assessment. A research assistant or the PI will complete the MOCA, with the participant with dementia. The caregiver will complete the NPI. Following Visit 2, an occupational therapist will be provided results of the COPM and ASP for participants of the individualized treatment arm. A sensory protocol will be developed based on assessment results following predetermined guidelines. All intervention materials for all study participants will be mailed to caregivers within 4 days of Visit 2. Upon receipt of intervention supplies, caregivers will contact the PI or occupational therapist for study initiation. Visit 3 will provide caregiver training for intervention use and initiation of Actigraph use. Adverse events since Visit 2 will be recorded. Visit 3 marks day 1 of intervention implementation. Participants will mail Actigraph back to UKADC in provided pre-paid envelop following week one of intervention.

Visits 4-8 will be scheduled at the end of each week following Visit 3. The PI, occupational therapist, or research assistant will record concurrent medication, and adverse events. With the caregiver, the interviewer will review behaviors observed by the caregiver, the behavior journal, compliance and acceptance of the intervention by the caregiver and the person with dementia. Actigraphs will be mailed from UKADC to participants, and patient will be asked to wear actigraph for last week of intervention window.

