## Statistical Analysis

Participants' characteristics were compared among the three arms using analysis of variance (ANOVA) for continuous measures and chi-square tests or Fisher's exact for categorical measures. The analysis of the primary endpoint used a chi-square test to compare the proportion of participants completing at least 75% of the video sessions among the study arms. The analysis of all secondary and exploratory endpoints relied on a modified intention-to-treat (mITT) strategy in which participants were included in the analysis only if the dyad completed at least one video session. For those endpoints, the main analysis tool was ANCOVA in which the mean value of an endpoint at the end of the intervention period was adjusted for baseline and then compared among the study arms. Sensitivity analyses were conducted in which multiple imputation was used for missing responses at the end of the intervention period (regressed on baseline) and in which the list of covariates included age of the person with AD at baseline and gender of the caregiver when appropriate. These sensitivity analyses did not change any of the conclusions drawn from the reported ANCOVA in Table 3 and are not reported here. A further sensitivity analysis included the measurements made at the four-week follow-up and relied on ANCOVA to compare the profile of responses at the end of the intervention and at the four-week follow-up each adjusted for baseline. This analysis did not change the conclusions drawn from Table 3 and is not reported here. All analyses were done using PC-SAS, Version 9.4.

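### Discretionary removal for undefined noncompliance, with replacement of early terminations, can bias the adherence result that this feasibility trial exists to measure

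*Combined protocol and SAP*

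**What the plan says.** Under Study Design, the primary measures open with "Feasibility will be assessed by monitoring of protocol adherence and behavior change". On the instrument, the text says "Adherence to the protocol will be kept and measured using the behavioral journal and intervention adherence log". The next item, on weekly check-ins, ends with the removal rule: "If the investigator finds that the participant is noncompliant, the PI" "may remove the participant from further participation in the study". No threshold, definition or independent check of noncompliance is given.

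Research Procedures states that "researchers will recruit for replacement participants so that the study is completed with 30 entire study duration cases". The trigger for this is worded as "In the event of drop out or early termination (causes will be recorded", so reasons for leaving are to be kept. Removal by the PI is not named as a trigger there, but it is not excluded either.

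The Data Analysis paragraph plans 10 dyads per arm and a per-protocol analysis at 75% adherence or more. The later Statistical Analysis section gives the primary test as a chi-square to "compare the proportion of participants completing at least 75% of the video sessions among the study arms". It defines a modified intention-to-treat set (at least one video session) for secondary and exploratory endpoints only. The set for the primary endpoint is not stated.

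On burden by arm, controls receive "Standard of care for behavioral management and 2-page educational pamphlet describing safety for home environments". The standard arm uses a sensory kit three times a day. The individualized arm uses one at two scheduled times a day and once more as needed.

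**The concern.** The quantity being measured is also a ground for ending its measurement. A dyad that struggles with the programme is what a feasibility trial needs to count. Under these rules the PI may end its participation, and a replacement may take its place. What the reported proportion then means depends on two things the documents leave open: how often the rule is used, and whether removed dyads stay in the denominator.

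The behavioural outcomes are exposed too. A Termination visit is described for participants who leave treatment because of adverse events, but none is described for removal for noncompliance. Dyads removed that way would probably lack end-of-intervention NPI, VABS, COPM and Zarit values, and those losses would be concentrated among poor adherers.

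**Working it through.** The plan gives no power calculation, expected adherence or expected removal rate. The only figure to reproduce is the total: 3 arms × 10 = 30, which agrees. Everything below uses assumed rates, shown as ranges.

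**Upward bias: only full-duration dyads counted.** Let p be the true share of randomised dyads that adhere, and r the share of non-adherers who are removed and replaced.

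- Share kept to the end: k = p + (1 − p)(1 − r)
- Adherence shown among completers: p / k
- Expected number randomised to obtain 10 completers in an arm: 10 / k

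For p = 0.70 and r = 0.50: k = 0.70 + 0.30 × 0.50 = 0.85. Adherence shown is 0.70 / 0.85 = 82%, and 10 / 0.85 = 11.8 dyads are randomised.

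| True p | r = 0 | r = 25% | r = 50% | r = 75% | r = 100% |
|---|---|---|---|---|---|
| 60% | 60% | 67% | 75% | 86% | 100% |
| 70% | 70% | 76% | 82% | 90% | 100% |
| 80% | 80% | 84% | 89% | 94% | 100% |
| Randomised per arm at p = 70% | 10.0 | 10.8 | 11.8 | 12.9 | 14.3 |

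**All randomised dyads counted.** If removed dyads are scored non-adherent, and would not have reached the threshold anyway, the estimate stays at p for any r. For example, with 14 randomised, 10 adherent and 4 removed, the result is 10/14 = 71%, against 10/10 = 100% among completers.

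**Downward bias: the video-session endpoint with removed dyads counted.** A poor kit user may still attend every session. Suppose an arm has 10 dyads, all of whom would reach 75% of sessions, and 3 of them use the kit poorly. If the PI removes 0, 1, 2 or 3 of these before they reach 75%, the arm shows 10/10, 9/10, 8/10 or 7/10. The shortfall comes from the removals alone.

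**Between-arm comparison.** Assume equal true adherence in all arms, removal and replacement only in the two active arms, a completers-only denominator, 10 per arm and a 3 × 2 Pearson chi-square at an assumed 0.05. Exact enumeration gives the chance of a spurious difference:

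| True p | r = 0 | r = 50% | r = 100% |
|---|---|---|---|
| 60% | 4% | 10% | 83% |
| 70% | 5% | 10% | 62% |
| 80% | 5% | 8% | 32% |

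This table treats adherence and endpoint success as the same thing and takes the asymmetry between arms as given. The documents establish neither, so it shows sensitivity and is not an estimate.

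**Secondary endpoints.** The modified intention-to-treat set nominally keeps a removed dyad that had one session. The main ANCOVA still needs an end-of-intervention value. The sensitivity imputation is described as a regression on baseline, with adherence not mentioned, so it does not address loss caused by poor adherence.

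**The case against.** Removal is discretionary, causes of early termination are recorded, and nothing in the documents shows that any dyad was removed for noncompliance. The study is declared not fully powered, and its behavioural results exploratory. All of that stands.

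A reader might infer more than the documents support in four ways:

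- **That the rule determines the feasibility result.** A reading of 100% needs every non-adherer to be removed and replaced, and only completers to be counted. With all randomised dyads in the denominator, replacement causes no inflation.
- **That the effect falls on the active arms only.** The daily kit regimen makes it likely that those arms are affected more, but this is an inference. Weekly visits and daily journals are described without distinction by arm, so a control dyad could also be judged noncompliant. The Control Group text offers a kit only after follow-up, while the Payment text says kits are mailed in all arms. The design is called single-blind without saying who is blinded, so the PI's knowledge of arm is also inferred.
- **That PI-removed dyads are certainly replaced.** This follows from the ordinary meaning of early termination; Research Procedures does not name such removals.
- **That kit adherence and the primary endpoint are the same.** Study Design uses the journal and log; Statistical Analysis uses video sessions. The completers-only percentages describe kit adherence and carry over to the video endpoint only if the two coincide.

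The stated maximum of 56 human subjects might also limit replacement. If it counts both members of a dyad it allows 28 dyads, fewer than the planned 30, so it is not a dependable constraint. If it counts patients only, even full removal in both active arms at 70% adherence (14.3 × 2 + 10 = 38.6) would fit.

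Finally, the file is marked closed and Statistical Analysis is in the past tense, so a change to the removal rule now matters mainly for reuse of the protocol.

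**Conclusion.** The concern holds as a risk of bias in either direction. Followed as written, the removal and replacement rules act on the primary feasibility construct, and the unstated denominator decides which way the result moves. With a completers-only denominator and an assumed true adherence of 70%, the overstatement runs from 6 percentage points (a quarter of non-adherers removed) to 30 (all removed). With every randomised dyad counted, replacement adds nothing, but removal can lower the video-session proportion. A heavier effect on the active arms is probable but not documented. Selective loss of week 4 data from poor adherers is a further consequence that the described imputation does not repair; its size cannot be given from the documents. The adherence and removal rates are assumptions throughout.

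**What to change.** 1. Separate under-use of the intervention from withdrawal from the study, and define noncompliance. Noncompliance alone should not end follow-up: the dyad is still offered the remaining video sessions and the Visit 9 and Visit 10 assessments. Removal for safety or at the dyad's request is unchanged.
2. Put every randomised dyad, including removed and replaced ones, in its arm's primary denominator, and state how a removed dyad is scored.
3. List removals and replacements by arm with the reason; causes are already to be recorded.
4. Reconcile the two definitions of adherence (journal and log, or video sessions), and the two statements on whether controls are mailed kits.

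If conduct is complete, apply items 2 and 3 to the existing data and label any completers-only result as such.

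The cost is a short protocol modification, a denominator statement and one listing, with no visits beyond those scheduled. Reported adherence may look less favourable, and some effort goes to following dyads who use the kit little.

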**Standard Environmental Design Protocol:** Participants' caregivers will receive standard recommendations for physical environmental modifications, caregiving techniques, and a sensorimotor stimulation kit via mailing from study site. Physical environmental modifications will include declutter living space, reduce background noise, increase natural light, accommodate for accessibility to commode and areas for drinking and eating. Caregiving techniques will include training for calming demeanor (emotional contagion), needs-driven care to decrease onset of behavioral disruption, and accepting and accommodating approach to behavioral disruption. A sensorimotor stimulation kit will be provided to each participants' caregiver for administration three times per day, lasting 30-60 minutes total per day. The stimulation kit will include an item for tactile tool via hands and arms, auditory input via a CD or audio file for music and speakers, olfactory input will be gained through use of scented oils on cotton balls, proprioceptive input will be provided with a 3 pound lap pad, vestibular input will be provided through written instruction of movement (walking, dancing, arm movements if unable to walk unassisted), and visual input via fiberoptic lights and a handheld liquid gel timer.

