**Individualized Environmental Design Protocol:** Participants' caregivers will receive standard recommendations of physical environment modifications and caregiving techniques. Physical environmental modifications will include declutter living space, reduce background noise, increase natural light, accommodate for accessibility to commode and areas for drinking and eating. Caregiving techniques will include training for calming demeanor (emotional contagion), needs-driven care to decrease onset of behavioral disruption, and accepting and accommodating approach to behavioral disruption. Individualized sensory stimulation kits will be developed using subjects' preferred sensory stimuli (as determined by the Adult Sensory Profile assessment) and behavioral concerns identified in the COPM. One target behavior and/or time period of the day will be targeted for improvement. Selection of items included in the individualized sensory kit will be determined based on the attached decision tree and sensory mode plans. The sensory kit will be provided via caregiver administration or supervision two scheduled times (once in the morning and once in the afternoon) per day and one time as needed prior to activity or task associated with behavior concern to promote maintained behavioral regulation and adaptive responses.

**Data Analysis:** Due to the nature of feasibility of this study, sample size of 30 participants with cognitive impairment (10 per arm) does not fully power the study. Statistical description of behavior change results will be explorative and descriptive in nature. Per-protocol analysis (PPA) will be performed with 75% or more adherence to program as determined from weekly visits and journals. Power analyses for secondary outcome measures cannot be performed as this study is a preliminary investigation of these secondary outcome measures.

Summary statistics will be tabulated for the behavior change, protocol adherence, and adverse events. The frequencies of behavior change, protocol adherence, and adverse events will be compared between participants within same group and between group for differences.

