#### Behavioral Journal

Behavior journals will be kept by caregivers daily during the 4-week intervention. Behavior journals will be used to measure adherence to the treatment protocol using a daily tracking log, prompt care partner reflection of each week's intervention use, and monitor behavioral changes throughout the intervention. Journals will be reviewed weekly with study personnel and returned to investigator at intervention completion on week 4 visit. Analysis will include quantitative

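### The protocol's 75% per-protocol set is not reconciled with the SAP's mITT set; programme adherence is undefined for controls and has no stated denominator in any arm

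*Combined protocol and SAP*

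**What the plan says.** **Analysis sets.** The Data Analysis section of the protocol's Research Description states: "Per-protocol analysis (PPA) will be performed with 75% or more adherence to program as determined from weekly visits and journals". It names no intention-to-treat or modified intention-to-treat set. Its closing paragraph plans to compare mean changes from baseline in each treatment group with the standard-care group by ANOVA.

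The SAP's Statistical Analysis section uses mITT for all secondary and exploratory endpoints: "participants were included in the analysis only if the dyad completed at least one video session". It describes no per-protocol analysis. The 75% figure appears there in the primary endpoint, whose test is to "compare the proportion of participants completing at least 75% of the video sessions among the study arms".

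**Measuring adherence.** Under Primary measures: "Adherence to the protocol will be kept and measured using the behavioral journal and intervention adherence log". Under Behavioral Journal: "Behavior journals will be used to measure adherence to the treatment protocol using a daily tracking log". Neither place gives a numerator or a denominator.

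**What each arm has to deliver over 4 weeks.**
- Standard arm: a kit "for administration three times per day, lasting 30-60 minutes total per day".
- Individualized arm: a kit used at "two scheduled times (once in the morning and once in the afternoon) per day and one time as needed prior to activity or task".
- Control: "Standard of care for behavioral management and 2-page educational pamphlet describing safety for home environments". A kit is offered only after the four-week follow-up visit. The Payment section, however, says that kits are mailed in every arm.

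**Who stays in.** Under Primary measures, the investigator may remove a noncompliant participant. Under Research Procedures, dropouts are replaced until 30 participants have completed the whole study.

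**The concern.** A set defined by adherence is chosen after randomisation. If the choice operates in two arms and has no counterpart in the third, the comparison with standard care is no longer between groups formed by chance. Caregivers who keep up a daily programme for four weeks may differ from those who do not in capacity, in burden, and in the behaviour of the person they care for. Those differences would be read as treatment effect.

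The same 75% also serves two purposes: in the protocol it is an inclusion rule on programme adherence, and in the SAP it is an outcome on session attendance. Nothing explains the change. An analyst following one document would work with a different group of dyads from an analyst following the other. With 10 dyads per arm, moving a few in or out can matter.

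**Working it through.** The 75% cut is a design choice, so there is no computed figure to reproduce. The sample size is consistent: 3 arms × 10 = 30.

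**Step 1: the sets side by side.**

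| | Protocol, Data Analysis | SAP, Statistical Analysis |
|---|---|---|
| Named set | Per-protocol, at least 75% adherence | mITT, at least one video session |
| Role of 75% | Inclusion rule | Primary endpoint |
| What 75% refers to | Programme, from visits and journals | Video sessions |
| Other document's set mentioned? | No | No |

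**Step 2: the control arm.** Under the Control Group section, no kit session is prescribed during the window. Adherence counted in kit sessions is then 0/0, which is undefined. Video-session attendance is defined for controls, but it is a different quantity.

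**Step 3: the denominator.** Inputs: 28 days (4 weeks); 3 uses per day in the standard arm; 2 scheduled uses plus 1 as needed per day in the individualized arm.

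- Standard arm: 3 × 28 = 84 occasions; 0.75 × 84 = 63 needed.
- Individualized arm, as-needed use counted as due every day (assumption): the denominator is 84. Delivering every scheduled session and no other gives 2 × 28 = 56, and 56/84 = 66.7%, below 75%. Entry needs 63 − 56 = 7 as-needed uses on top of perfect scheduled delivery: 62/84 = 73.8% is out, 63/84 = 75.0% is in.
- Individualized arm, scheduled uses only: 56/56 = 100%; 0.75 × 56 = 42 are enough.
- Individualized arm, scheduled uses plus the as-needed occasions that arose, none of the latter delivered:

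| As-needed occasions that arose | Score | At 75% or above? |
|---|---|---|
| 0 | 56/56 = 100% | Yes |
| 7 | 56/63 = 88.9% | Yes |
| 14 | 56/70 = 80.0% | Yes |
| 28 | 56/84 = 66.7% | No |

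The same dyad is therefore in or out according to a choice that is not written down. As-needed use is tied to tasks linked with the behaviour of concern. Under the 84 denominator, inclusion would thus depend partly on how often such occasions arise, which is close to the outcome under study.

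**Step 4: possible size of the imbalance.** The documents give no adherence rate. If a fraction f of active dyads falls below 75%, 10 × (1 − f) remain per active arm:

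- f = 10%: 9 per active arm against 10 controls
- f = 30%: 7 against 10
- f = 50%: 5 against 10

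**The case against.** Several stronger readings are tempting, and the documents do not support them.

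- *A reader might infer that the two documents flatly contradict each other.* The protocol says that a per-protocol analysis will be done. It does not call it the only or the main analysis, and the closing paragraph of Data Analysis states no adherence restriction. A per-protocol analysis alongside an unrestricted one is compatible with that text. What stands is an unexplained difference.
- *A reader might infer that the 75% rule cannot be applied to controls at all.* The rule also draws on weekly visits, and neither visits nor journals are limited to the active arms. The SAP applies a 75% attendance criterion in every arm, and the Payment section mentions kits for all arms. Control adherence is undefined, not impossible to define.
- *A reader might infer that fully compliant individualized-arm dyads will be excluded.* That follows only if the as-needed use is due daily, which no section states. Not using it when no need arises is arguably the more natural reading of adherence. The programme also includes home modifications and caregiving techniques, which a session count ignores. The detailed protocol, journal and adherence log are attachments outside the supplied text and may define the measure.
- *A reader might infer that the SAP's comparisons suffer from the adherence filter.* The SAP describes no per-protocol analysis, so the selection argument applies to the protocol's set.
- *A reader might treat the one-session mITT condition as equally serious.* It also conditions on attendance, but lightly. The number excluded is not given, and it is not said which visits count; screening and baseline are also held by Zoom.

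A labelled supportive per-protocol analysis is legitimate in an unpowered feasibility study. That is a reason not to insist on deleting it, but not a reason to use it for comparing arms.

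**Conclusion.** The point holds in a limited form. The only set named in the protocol is absent from the SAP, and the only set named in the SAP is absent from the protocol. Used for the comparison with standard care, the protocol's set would select active-arm dyads on post-randomisation adherence without an equivalent selection in control. This rests on the Control Group section being the operative description; its conflict with the Payment section must be reconciled.

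The swing between 67% and 100% shows what the missing denominator can do. It is a conditional risk, not a demonstrated exclusion. The range of 9 to 5 retained dyads per active arm rests wholly on the assumed 10% to 50%; the actual loss is unknown. The primary endpoint on video-session completion is not affected by this point. The change should be made, in proportion to a study that calls its own behavioural results exploratory.

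**What to change.** 1. State in both documents which analysis set serves which endpoint, and explain the move from per-protocol to mITT.
2. Base all between-arm comparisons on every randomised dyad in its assigned arm, including those later replaced or removed. Use the multiple imputation that the SAP already describes, which regresses on baseline, wherever a baseline value exists. Report by arm the dyads without one.
3. Do not use the 75% per-protocol set for between-arm inference. Report 75% programme adherence descriptively within the active arms, with scheduled occasions as the denominator (84 in the standard arm, 56 in the individualized arm). Tabulate as-needed uses separately.
4. Keep programme adherence and video-session attendance as two separately named quantities, and say which visits count as video sessions.
5. Reconcile the Control Group and Payment sections on whether and when controls receive a kit.

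The cost is wording in both documents and a re-run of the existing analyses, with no new data collection. The downside is that estimates may be diluted by low adherers.

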Summary statistics will be tabulated by treatment arm for the baseline, week 4, and week 8 outcome measures of VABS, NPI, and protocol adherence based on behavior journals. The change from baseline to week 4 and follow-up will be calculated for each patient. Descriptive statistics will be examined to see whether levels of each assessment at baseline are normally distributed. If they are, then the mean changes will be compared in each treatment group with the standard of care group by analysis of variance (ANOVA). If they are not normal, then consideration will be given to data transformation.

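### The protocol judges normality on baseline levels, which neither its change-score ANOVA nor the SAP's ANCOVA assumes, and the move between the two models is not explained

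*Combined protocol and SAP*

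**What the plan says.** **Protocol, Research Description, Data Analysis.** VABS, NPI and adherence are to be summarised by arm at baseline, week 4 and week 8. "The change from baseline to week 4 and follow-up will be calculated for each patient". The next step is the distribution check: "Descriptive statistics will be examined to see whether levels of each assessment at baseline are normally distributed". If the check is satisfied, "the mean changes will be compared in each treatment group with the standard of care group by analysis of variance (ANOVA"). If it is not, transformation is to be considered. The text does not say which transformation, whether it applies to levels or to changes, or which test would follow. It does not mention the distribution of the changes or of the residuals.

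The same section limits its own ambitions: "sample size of 30 participants with cognitive impairment (10 per arm) does not fully power the study", and "Statistical description of behavior change results will be explorative and descriptive in nature".

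**SAP, Statistical Analysis.** On every secondary and exploratory outcome the SAP reports that "the main analysis tool was ANCOVA in which the mean value of an endpoint at the end of the intervention period was adjusted". The adjustment is for the baseline value, and all three arms enter the comparison. There is no normality rule, no transformation and no change-score ANOVA. The primary endpoint, completion of at least 75% of video sessions, is compared by chi-square.

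**Overlap.** The protocol's Study Design text lists VABS and NPI as secondary measures, so both analysis descriptions apply to them.

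**The concern.** Two things look wrong.

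First, the check looks at the wrong variable. An ANOVA on change scores needs roughly normal deviations of the changes around their arm means. An ANCOVA conditions on baseline and needs roughly normal residuals given baseline. Neither places any condition on the marginal distribution of baseline. A baseline check can therefore prompt a transformation that the model does not need, and can pass data whose residuals are clearly skewed. An unneeded transformation also moves the result off the scale on which VABS and NPI are read.

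Second, the protocol and the SAP name different models for the same continuous outcomes, and nothing in the available text says when or why one replaced the other. At 10 per arm the choice affects precision. A reader also cannot tell whether ANCOVA was chosen before the data were seen.

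**Working it through.** **Inputs from the documents.** Three arms, 10 per arm: "Recruitment will be ongoing until all groups have 10 participants". So 3 × 10 = 30, which agrees with the stated total. No other figure can be reproduced: "Power analyses for secondary outcome measures cannot be performed as this study is a preliminary investigation". The documents give no alpha, SD, effect size or baseline-to-follow-up correlation *r*.

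**Assumed for illustration.** Shapiro-Wilk at 0.05 as a stand-in for inspecting descriptive statistics; gamma (shape 2) or exponential for skewed shapes; *r* from 0.3 to 0.9; no treatment effect.

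**Step 1. Does a baseline check track the model assumption?** Simulation, 3 × 10:

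| Scenario | Baseline flagged | Residuals flagged |
|---|---|---|
| Gamma(2) baseline, normal ANCOVA errors, *r* = 0.5 | about 75% | ANCOVA about 5% |
| Normal baseline, gamma(2) ANCOVA errors, *r* = 0.5 | about 5% | ANCOVA about 55% |
| Exponential baseline, normal changes | 96.7% | change 4.9% |
| Normal baseline, exponential changes | 5.0% | change 85.0% |

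In the gamma scenarios with *r* from 0.3 to 0.7, the change-score residuals are flagged in 6–9% of runs when only baseline is skewed, and in 21–37% when the ANCOVA errors are skewed. The direction is the same throughout. The check fires when the model is sound and stays at its 5% floor when it is not. The exact rates depend on the assumed shape.

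**Step 2. Does this damage type I error?** Change-score ANOVA on the raw data, nominal 5%: 5.2% with exponential baseline and normal changes, 3.8% with exponential changes, and 4.8% with gamma(2) errors at *r* = 0.5. There is no inflation.

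**Step 3. What does the choice of model cost in precision?** Take equal variances σ² at both times. The variance of a difference between two arms with *n* = 10 is:

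- change score: (2/*n*) · 2σ²(1 − *r*)
- ANCOVA: (2/*n*) · σ²(1 − *r*²) · [1 + 1/(*N* − *g* − 2)], where *N* = 30 and *g* = 3. The bracket is the price of estimating the slope: 1 + 1/25 = 1.04.

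The ratio, ANCOVA to change score, is (1 + *r*)/2 × 1.04:

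| *r* | (1 + *r*)/2 | × 1.04 | Change-score *n* per arm to match ANCOVA with 10 |
|---|---|---|---|
| 0.3 | 0.65 | 0.68 | 10/0.676 = 14.8 |
| 0.5 | 0.75 | 0.78 | 10/0.78 = 12.8 |
| 0.7 | 0.85 | 0.88 | 10/0.884 = 11.3 |
| 0.8 | 0.90 | 0.94 | 10/0.936 = 10.7 |
| 0.9 | 0.95 | 0.99 | 10/0.988 = 10.1 |

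Simulated ratios at 3 × 10 agree to about 0.01 (0.68–0.69, 0.78 and 0.88–0.89 for the first three rows).

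**Step 4. The two texts side by side.**

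| | Protocol, Data Analysis | SAP, Statistical Analysis |
|---|---|---|
| Outcome variable | change from baseline | end-of-intervention value |
| Model | ANOVA | ANCOVA on baseline |
| Contrast | each treatment arm v standard of care | among the arms |
| Week 8 | planned change | sensitivity analysis only |
| Distribution rule | baseline levels | none |

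**The case against.** **There is no hard gate.** The protocol speaks of examining descriptive statistics and of considering a transformation; it names no test and no threshold. This stands. The 75% and 96.7% figures belong to an assumed rule and show only which way the check points. It still points at the wrong variable, whatever form it takes.

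**Validity is hardly touched.** This also stands. A reader might infer that skewed residuals passing unnoticed would produce false positives; Step 2 does not bear that out.

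**Entry criteria do not make the baseline scores skewed.** It is tempting to argue that requiring a CDR of 1.5 or more and caregiver-reported behavioural challenges truncates the baseline scores. Neither criterion sets a cut-off on VABS or NPI, and the documents give no baseline distributions. Skewness is possible but undocumented.

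**Two live options?** A reader might conclude that both models remain open and the better result can be picked. The SAP is written in the past tense, refers to a results table and says the sensitivity analyses left the conclusions unchanged. It describes a completed analysis. What the text supports is an unexplained move, not two competing plans. A detailed protocol attachment is mentioned but is not part of the available text, and it may give the reason.

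**The large-sample precision formula flatters ANCOVA.** True at 10 per arm, so the factor 1.04 is included above. The gain has almost vanished at *r* = 0.9.

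**Conclusion.** The point holds, as a minor one. The protocol's distribution rule uses a quantity that neither of the two models assumes, and the available text does not account for the move from change-score ANOVA to baseline-adjusted ANCOVA.

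The consequence is possible needless transformation, missed residual skewness and, if the change-score plan were followed, lost precision. ANCOVA has roughly 0.7 to 0.9 of the change-score variance for *r* between 0.3 and 0.7, and close to the same variance at *r* = 0.9. These sizes rest on assumed correlations, equal variances at both times, and assumed test and shapes for the normality illustration.

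The phrase main analysis should not be taken to mean the primary endpoint: the chi-square comparison of session completion does not depend on any of this. No stated figure in the plan is wrong, and no confirmatory claim depends on the rule, since the protocol treats the behaviour results as exploratory.

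**What to change.** In the protocol's Data Analysis text, delete the rule that looks at normality of baseline levels. In both documents, name the SAP's baseline-adjusted ANCOVA as the single main analysis of the continuous secondary and exploratory endpoints. Judge distribution on the residuals of that model, with one residual plot per endpoint. State openly that this departs from the change-score ANOVA in the protocol, with the reason and, if it is on record, the date of the decision.

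A robust companion such as a permutation p-value is optional. If used, report it as a sensitivity analysis beside the ANCOVA; making it a switch after inspection of the residuals would bring back the data-dependent choice.

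The cost is a few sentences and the plots. It needs no new data, participants or visits.
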